### **V. Study Objectives:**

This study comprises three main objectives. First, to establish a treatment process and environment for utilizing rTMS to modulate neural activity in patients with upper limb hemiparesis caused by stroke. Second, to investigate the application of inhibitory stimulation, continuous theta burst stimulation (cTBS), to the unaffected hemisphere of the stroke-damaged brain, followed by

facilitatory stimulation, intermittent theta burst stimulation (iTBS), to the affected hemisphere. The intention is to employ the established treatment process in the first part to formulate a clinical treatment model. Third, we will further study functional assessments of the upper limb before treatment, immediately post-treatment, and at 1- and 3-month follow-ups.

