## VI. Study Design

- Duration of Treatment

- A. The experiment for establishment of therapeutic environment.

Participants in the experiment for establishment of therapeutic environment underwent 1-3 evaluations. During this experiment, repetitive Transcranial Magnetic Stimulation (rTMS) was employed for brain modulation, involving two sets of stimuli. Each set consisted of initially administering continuous Theta Burst Stimulation (cTBS) to suppress the healthy side (approximately 600 pulses), followed by intermittent Theta Burst Stimulation (iTBS) to enhance the lesion side (600 pulses), totaling approximately 4 minutes (around 1200 pulses). The intensity of iTBS and cTBS is 80-120% of Motor Threshold.

Patients receiving rTMS treatment concurrently underwent machine-assisted bilateral upper limb training. During treatment sessions, patients were instructed to repeatedly perform grasping-opening tasks or engage in bilateral upper limb activities involving simultaneous shoulder and elbow movements while counting down loudly from 300. Upon completion of all training sessions, patients and therapists were required to complete usability and satisfaction analyses to evaluate equipment usability and operational satisfaction.

- B. The experiment for evaluation of therapeutic effects.

Patients will be divided into three groups: a Control group, an rTMS group, and an rTMS+BT group. Each group will receive a 65-minute treatment session, administered once every two days, totaling 10 sessions and completing the entire course within 20 days.

Control group: only received traditional rehabilitation training for 50 minutes and self-stretching training (15 minutes); rTMS group: received rTMS intervention (15 minutes) and 50 minutes of traditional rehabilitation training; rTMS+BT group: received rTMS intervention (15 minutes) along with BT meanwhile and 50 minutes of traditional rehabilitation training.

- Number of Planned Patients

72 participants are expected to be recruited in the trial.

- Investigational Product

1. Robot-assisted palm and finger rehabilitation device

Device name: "RM" Wearable Powered Hand Rehabilitation Device (Non-Sterile)

Manufacturer: Rehabotics Medical Technology Corporation

2. Bilateral proximal/distal upper limb training platform

- (1) The name of proximal upper limb training device: Non-powered upper limb proximal training platform

Manufacturer: Rehabotics Medical Technology Corporation

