- (2) The name of distal upper limb training device: Non-powered upper limb distal training equipment

Manufacturer: developed equipment by the Rehabilitation Department of Chang Gung Hospital

3. Repetitive transcranial magnetic stimulation (rTMS)

Device name: Repetitive transcranial magnetic stimulation (rTMS)

Manufacturer: Apollo Powermag 100, Mag & More, Germany.

- Endpoints

The primary endpoint was evaluated through the Fugl-Meyer Assessment, while secondary endpoints encompassed various measures, including the Modified Ashworth Scale (MAS), Manual Muscle Testing (MMT) for the upper extremity, Action Research Arm Test (ARAT), Brunnstrom Recovery Stage, Instrumental Activities of Daily Living Scale (IADLs). Additionally, participants and therapists responded to the System Usability Scale (SUS) questionnaire, and a Satisfaction questionnaire was administered.

- Criteria for Evaluation

1. Inclusion Criteria

- (1) Demographics and baseline characteristics of the participants were all available.

- (2) Participants completed all treatment sessions.

- (3) Functional assessments of the upper limb were performed at multiple time points: prior to, immediately after, and at 1 and 3 months follow-ups, without any omissions.

- (4) Both participants and therapists completed the System Usability Scale (SUS) questionnaire and the Satisfaction questionnaire.

2. Exclusion Criteria
  - (1) Participants with unforeseen psychological issues or significant changes in health conditions to prevent interference with the analysis.
  - (2) Participants using non-study-related medications that could potentially interfere with the outcomes.

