### ● Statistical Methods

Detailed demographic and medical history records are documented for each subject, including age, gender, time of stroke onset, location of stroke, and types of stroke. The clinical assessment will be conducted by a licensed occupational therapist with experience in treating neurological conditions. Clinical assessment results are being compared between groups using a student-t test. Pre and post-training within each group are being assessed using one-way ANOVA to determine improvement. One-way ANOVA is employed for inter-group comparisons, followed by post-hoc tests. If the data do not follow a normal distribution, non-parametric statistical methods are applied. Correlation analysis is used to explore relationships between clinical assessment results and various factors. Quantitative data are presented as (Mean±SEM), and a 95% confidence interval ( $p<0.05$ ) is considered statistically significant.

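### Within-group improvement is to be tested with one-way ANOVA, which treats each patient's before and after scores as if they came from different people; as written, the test is too conservative and loses power.

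*Protocol*

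**What the plan says.** In the Protocol, section VI (Study Design), Statistical Methods, the test for change over time is fixed as follows: "Pre and post-training within each group are being assessed using one-way ANOVA to determine improvement". The next sentence gives the same method for the comparison between arms: "One-way ANOVA is employed for inter-group comparisons, followed by post-hoc tests". The fallback is general: "If the data do not follow a normal distribution, non-parametric statistical methods are applied". A p-value below 0.05 "is considered statistically significant".

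The data structure is set out elsewhere. Section V (Study Objectives) plans "functional assessments of the upper limb before treatment, immediately post-treatment, and at 1- and 3-month follow-ups". Under Criteria for Evaluation in section VI, a patient is evaluated only if assessments were "performed at multiple time points: prior to, immediately after, and at 1 and 3 months follow-ups, without any omissions". Every evaluated patient therefore contributes a score at each of four visits.

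On size, section VI says "72 participants are expected to be recruited in the trial", and the therapeutic-effect experiment has three groups. No SD, expected change, within-patient correlation or power calculation is given.

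**The concern.** One-way ANOVA without further qualification assumes that the sets of scores being compared are independent. Here they are not: each patient has a score before and after treatment. Scores on a motor scale such as the Fugl-Meyer Assessment differ between patients, and a patient who starts high will tend to finish high. A paired or repeated-measures analysis removes that stable difference from the error term. One-way ANOVA leaves it in.

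The result is a standard error for the change that is too large, a real type I error below the nominal 5%, and lost power. A real moderate gain in a group could be reported as no significant improvement when the same data, analysed as paired, would show it. This is the only test the protocol names for improvement within a group, and evaluating rehabilitation outcome across these visits is one of its stated aims.

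**Working it through.** The plan has no figure of its own to reproduce apart from the nominal 0.05, so the check compares the named test with a paired test under stated assumptions.

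**Inputs from the Protocol:** 72 participants, three groups, the same patients at each visit, significance at p<0.05.

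**Assumptions (not in the Protocol):** 72 / 3 = 24 analysed per group; equal SD at each visit, taken as the unit; two-sided test; within-patient correlation ρ of 0.5, 0.7 or 0.8; true change of 0.3, 0.5 or 0.8 SD.

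**Step 1: standard errors.** With two visits, one-way ANOVA is identical to the two-sample t-test (F = t²).

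- Standard error used by the test: SD × √(2/n) = √(2/24) = 0.289 SD.
- True standard error of the mean change: SD × √(2(1−ρ)/n) = 0.204, 0.158 and 0.129 SD at ρ = 0.5, 0.7 and 0.8.
- Inflation: 1/√(1−ρ) = 1.4, 1.8 and 2.2.

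**Step 2: observed change needed for p<0.05.** t(0.975, 46) × √(2/24) = 2.013 × 0.2887 = 0.581 SD. This does not depend on ρ, because the test ignores ρ.

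**Step 3: real type I error.** The normal approximation 2 × (1 − Φ(1.96/√(1−ρ))) gives 0.56%, 0.03% and 0.001% at the three correlations. Simulation with the t distribution (200,000 replicates per cell, bivariate normal) gives 0.7%, 0.1% and 0.01%. The paired test holds about 5% throughout.

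**Step 4: power by simulation, one-way ANOVA against paired t-test, n = 24.**

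| True change | ρ = 0.5 | ρ = 0.7 | ρ = 0.8 |
|---|---|---|---|
| 0.3 SD | 9.9% vs 29% | 5.5% vs 44% | 3.3% vs 61% |
| 0.5 SD | 36% vs 65% | 33% vs 86% | 31% vs 96% |
| 0.8 SD | 85% vs 96% | 90% vs 99.8% | 93% vs >99.9% |

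Hand check of one cell (0.5 SD, ρ = 0.7): Φ((0.5 − 0.581)/0.158) = Φ(−0.51) ≈ 0.30, against 0.33 simulated. The approximation treats the SD as known, which accounts for the small gap.

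**Step 5: sensitivity.**

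- Weaker correlation (ρ = 0.3, n = 24): type I error 2.1%; power at 0.5 SD 38% vs 51%.
- Stronger correlation (ρ = 0.9, n = 24): power at 0.5 SD 27% vs >99%.
- Large change (1.0 SD, n = 24, ρ = 0.3 to 0.9): a loss of about 2 points or less.
- Fewer patients, n = 20, ρ = 0.7: 24% vs 78% at 0.5 SD.
- Fewer patients, n = 18: threshold t(0.975, 34) × √(2/18) = 2.032 × 0.333 = 0.677 SD. At ρ = 0.7, power is 21% vs 73% at 0.5 SD and 73% vs 99% at 0.8 SD.
- If the sentence is meant to cover all four visits (n = 24, ρ = 0.7 between any two visits, 0.5 SD gained and fully kept): 18% vs 90% for repeated-measures ANOVA.

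Two separate simulations, one with 200,000 and one with 20,000 replicates per setting, agree on the two-visit results for 24 per group.

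**The case against.** The strongest reply is that the authors meant repeated-measures ANOVA. An analysis with visit as its single within-patient factor is also a one-way design, and synopses often shorten the name. That is possible. But the text does not say so, and the adjacent sentence uses the identical term where the groups really are independent. Even on the generous reading, the sentence does not tell the analyst which test to run and needs the same edit.

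A second reply is that details belong in the SAP. That holds for the exact non-parametric test, and leaving that test unnamed is not a fault in itself. The fallback also does not cure the problem, because it depends on non-normality and not on pairing. The parametric test is different: the protocol names it, and an SAP using a paired method would contradict the protocol.

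A third reply concerns weight, and much of it stands. Change within one arm cannot separate the study treatment from usual rehabilitation or natural recovery, so this is not the treatment comparison. The error is conservative. Every magnitude rests on assumed inputs, and for changes near 1 SD the loss almost disappears. The figure of 24 per group also assumes that all 72 participants enter the therapeutic-effect experiment, although the study also has an earlier set-up experiment; with fewer patients the pattern is the same. The four-visit figure goes beyond the sentence, which speaks only of before and after training, and is secondary.

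**Conclusion.** The concern holds. As written, the protocol names a test for independent groups for a comparison of repeated measurements on the same patients. The direction follows from positive within-patient correlation alone: the test is conservative and loses power.

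The size depends on the assumptions listed above. For correlations of 0.5 to 0.8 with 24 per group, the real type I error lies between 0.7% and 0.01%. Power at a 0.5 SD change falls from 65–96% to 31–36%. The loss is severe for true changes below about 0.6 SD and modest at 0.8 SD.

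The reach is limited to the parametric within-group tests of improvement. The comparison between arms is unaffected, and no false claim of improvement is created. It should be fixed, but it does not threaten the trial's main comparison.

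**What to change.** Replace the sentence on within-group testing with one that names a single method and a single contrast. For a before-versus-after comparison, for example:

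> Change from before to immediately after treatment within each group is assessed with a paired t-test, or the Wilcoxon signed-rank test if the differences are not normally distributed, and is reported as mean change with a 95% CI.

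If change across all four visits is intended, name either a repeated-measures ANOVA or a linear mixed model with a patient effect, give Friedman's test as the non-parametric counterpart, and state which visit contrast is of interest. These methods answer different questions, so the protocol should commit to one.

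The sentences on comparisons between groups need no change for this point. The cost is one sentence: the same patients, visits and data, and standard software.

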## II. Indication

### 1. Inclusion Criteria

- (1) Age 40-80 years;
- (2) First-onset stroke patients;
- (3) Patients diagnosed with cerebral infarction or hemorrhage through CT or MRI;
- (4) Signed informed consent form by the patient and their family;
- (5) Stable physiological parameters;
- (6) Stroke occurred within the last 12 months;
- (7) Patients with unilateral hand function impairment caused by the stroke;
- (8) Upper limb muscle tone (Modified Ashworth Scale, MAS) less than 3 points;
- (9) Able to follow two-step commands.

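### The within-group pre/post test is the only analysis given the job of determining improvement, and the protocol does not say that efficacy rests on the comparison with Control

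*Protocol*

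**What the plan says.** Statistical Methods (Protocol, section VI) names three analyses of the clinical assessments. The one that matters here is the second in order: "Pre and post-training within each group are being assessed using one-way ANOVA to determine improvement". It is the only one that comes with a purpose.

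The sentence before it plans a Student t test between groups. The sentence after it reads "One-way ANOVA is employed for inter-group comparisons, followed by post-hoc tests". Both name a test but do not say what it decides.

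Four other places bear on how a pre/post change can be read:

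- Inclusion criterion (6): "Stroke occurred within the last 12 months". There is no lower limit on time since stroke.
- Study Design, part B: "Patients will be divided into three groups: a Control group, an rTMS group, and an rTMS+BT group". A concurrent comparator therefore exists. Its content is given as "Control group: only received traditional rehabilitation training for 50 minutes and self-stretching training (15 minutes", and both rTMS arms also receive 50 minutes of traditional rehabilitation per session.
- The length of treatment: "totaling 10 sessions and completing the entire course within 20 days".
- Study Objectives: "functional assessments of the upper limb before treatment, immediately post-treatment, and at 1- and 3-month follow-ups". There is one assessment before treatment.

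Time of stroke onset is recorded. The protocol states no stratification by it and no adjustment for it.

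**The concern.** A change inside one arm is the sum of everything that happened to its patients between two assessments: natural recovery, traditional rehabilitation, familiarity with the test, and any effect of rTMS or BT. Entry is open from soon after the stroke, and all arms receive the same 50 minutes of rehabilitation, so the first two parts may well be above zero in every arm, Control included. A pre/post test cannot separate them from the last part. This is true of a correct paired test as well, so the point is about what the test is used to decide and not about which test is named.

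Part B is described as evaluating therapeutic effects, and the objectives aim at a clinical treatment model. Both need the gain over Control. If the within-group result is taken as the answer, two misreadings are open. One is to call an active arm effective because it improved. The other is to call it effective because it reached significance and Control did not.

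**Working it through.** The protocol gives no expected gain, SD, effect size or power for this analysis, so there is no planned figure to reproduce. The size of the risk has to be shown under assumptions.

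**Inputs from the protocol.** Three groups, 72 participants in total, significance at p < 0.05, Fugl-Meyer as primary endpoint.

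**Assumptions.** Equal groups, 72 / 3 = 24 each (neither the allocation ratio nor the share of the 72 used in part A is stated). Two-sided test. Background gain of 2, 3 or 5 points and SD of change of 5 or 8 points. Zero treatment effect in every arm.

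**Step 1. Chance that one arm shows a significant gain, paired test.** Power comes from the noncentral t distribution with 23 degrees of freedom, noncentrality (gain / SD) × √24, critical value 2.069. Example: gain 3, SD 5 gives 0.6 × 4.899 = 2.939 and probability 0.804.

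| Background gain | SD of change 5 | SD of change 8 |
|---|---|---|
| 2 points | 0.467 | 0.217 |
| 3 points | 0.804 | 0.421 |
| 5 points | 0.997 | 0.834 |

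**Step 2. Chance of a misleading contrast.** Let p be the probability from step 1. With independent arms, at least one of the two active arms is significant while Control is not with probability (1 − p) × [1 − (1 − p)²]. Example: p = 0.467 gives 0.533 × (1 − 0.284) = 0.38.

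| Background gain | SD of change 5 | SD of change 8 |
|---|---|---|
| 2 points | 0.38 | 0.30 |
| 3 points | 0.19 | 0.39 |
| 5 points | 0.003 | 0.16 |

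This is low only where nearly every arm is significant.

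**Step 3. The test as literally named.** A one-way ANOVA on pre and post values treats them as independent samples. Both versions were simulated (20,000 runs, three arms of 24, no treatment effect, the same background gain in every arm, pre-post correlation 0.7 to 0.95). Here gains are in SDs of the score, not of the change. Chance that one arm is significant:

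| Background gain | One-way ANOVA, unpaired | Paired test |
|---|---|---|
| 0.2 SD | 0 to 1.6% | 23 to 85% |
| 0.3 SD | 0.3 to 5.7% | 44 to 99% |
| 0.5 SD | 24 to 33% | 86 to 100% |
| 0.8 SD | 90 to 98% | nearly 100% |

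The literal test seldom flags small gains and often flags large ones. Correcting the pairing alone would make a background gain more visible, so the two repairs belong together.

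**Step 4. The comparison between groups.** In the same simulation, one-way ANOVA across the three arms, on change or on post values, was significant in 4.7 to 5.3% of runs for every background gain from 0 to 0.8 SD. The arms were comparable by construction. In the trial, this protection depends on the groups being alike in time since stroke.

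**The case against.** The strongest reply is that the control comparison is already planned. The within-group sentence stands between two sentences on comparisons between groups, and part B has a concurrent Control group. This stands. A reader might infer that the within-group test is the protocol's rule for efficacy, and the documents do not support that.

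Second, the text speaks of improvement, not of improvement due to treatment. Asking whether patients changed is a legitimate descriptive question, and nothing says that a within-group result will be reported as efficacy. A reader might infer that spontaneous recovery would be declared a treatment effect. That is a prediction about reporting which the text does not bear out; it could happen, and no more can be said.

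Third, the step 1 probabilities are not error rates in themselves. In those scenarios the arm really did gain 2 to 5 points, so they are power to detect a true change. They become error rates only once the change is attributed to treatment. They also rest on a paired test, which the protocol does not name. Both parts stand.

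Fourth, the sentence covers pre against post training, about 20 days, so recovery over the 3-month follow-up should not be counted in. Nor is the lack of a run-in a fault: with a concurrent control, individual recovery slopes are not needed for the treatment contrast.

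Fifth, ranking confirmatory and descriptive analyses is often left to the SAP. This holds for a protocol that is silent. This one attaches the word improvement to one analysis, the one that cannot isolate treatment, and gives the others no stated role. That is a purpose badly fixed, not a detail left open.

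**Conclusion.** The point holds in a limited form. The protocol assigns the determination of improvement to a pre/post test within each group and does not say that efficacy rests on the between-group comparisons that it also lists. With entry at any time up to 12 months after stroke and traditional rehabilitation in all arms, a significant within-group change could be taken for a treatment effect when rTMS or BT adds nothing.

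Under the stated assumptions, an arm without treatment effect would show a significant gain with probability 0.22 to 0.997 in a paired test. With the literal unpaired ANOVA, the chance is small for gains up to about 0.3 SD and substantial from about 0.5 SD. The gains, SDs, correlations and group size are all assumed, so the width of the range is part of the result. The direction does not depend on them: the within-group result moves with background recovery, while the comparison of comparable groups stays at about 5%. The planned comparison with Control limits the harm, and a change of wording removes the ambiguity.

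**What to change.** Replace the within-group sentence in Statistical Methods with:

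> Improvement attributable to treatment is determined by the between-group difference in change in Fugl-Meyer score from the pre-treatment assessment, adjusted for the baseline score and time since stroke. Within-group changes are reported descriptively as mean change with 95% CI.

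The adjustment matters because the comparison with Control guards against background recovery only when the groups are alike in time since stroke, and the protocol states nothing else to secure this. Both covariates come from data already collected: the pre-treatment assessment and the recorded time of onset.

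The cost is small. No patients, visits or measurements are added. The between-group analysis becomes a covariate-adjusted model in place of an unadjusted t test or one-way ANOVA, which is a modest change to the stated method. The downside for the sponsor is that significant within-group results can no longer be presented as evidence of efficacy.

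### The between-group FMA comparison is fixed as an unadjusted t test and one-way ANOVA, leaving the required pre-treatment assessment unused as a covariate

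*Protocol*

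**What the plan says.** Protocol, section VI, Statistical Methods, gives two between-group methods: "Clinical assessment results are being compared between groups using a student-t test" and "One-way ANOVA is employed for inter-group comparisons, followed by post-hoc tests". The fallback is "If the data do not follow a normal distribution, non-parametric statistical methods are applied". The only stated use of the pre-treatment value is within groups: "Pre and post-training within each group are being assessed using one-way ANOVA to determine improvement". Neither a baseline covariate nor a mixed model appears anywhere, and the text does not say whether post-treatment scores or changes from baseline are compared.

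Under Endpoints, "The primary endpoint was evaluated through the Fugl-Meyer Assessment". Under Criteria for Evaluation, inclusion item (3) requires upper-limb assessments "prior to, immediately after, and at 1 and 3 months follow-ups, without any omissions". That item does not name the scale. That it includes the FMA is an inference, though a natural one, since the same item covers the visits at which the primary endpoint must be measured.

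The planned size is stated as "72 participants are expected to be recruited in the trial", with no effect size, SD, power or allocation ratio. The significance level is 0.05.

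**The concern.** A t test and a one-way ANOVA use group as the only explanatory variable. Where baseline and follow-up scores are correlated, part of the follow-up variance is predictable from baseline, and an unadjusted comparison of post scores leaves it in the error term. A comparison of change scores does use baseline, but with its coefficient forced to 1. That costs precision when the correlation is low or when follow-up scores vary less than baseline scores. Analysis of covariance estimates the coefficient from the data.

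In a three-arm trial of 72 patients, wasted precision matters. The protocol gives neither the correlation nor the SDs, so it offers no ground for relying on either unadjusted form. Because the tests are named, this is a stated choice and not a detail left open for the SAP.

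**Working it through.** **Inputs from the protocol.** Total 72; three groups; significance level 0.05. The 72 cannot be reproduced, because no design assumptions accompany it.

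**Assumptions, not in the protocol.** All 72 enter the therapeutic-effects experiment, 24 per arm, with no losses; random allocation; two-sided testing; true pairwise difference 0.5 follow-up SD; baseline-to-follow-up correlation ρ from 0.3 to 0.9; ratio k = follow-up SD / baseline SD of 0.8, 1 or 1.25.

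**Variance per patient, follow-up SD set to 1.**
- Post score: 1
- Change score: 1 + 1/k² − 2ρ/k, which is 2(1 − ρ) at k = 1
- Baseline-adjusted: 1 − ρ²

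**Variance of the adjusted comparison relative to each alternative.**

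| ρ | 0.3 | 0.5 | 0.7 | 0.8 | 0.9 |
|---|---|---|---|---|---|
| vs post | 0.91 | 0.75 | 0.51 | 0.36 | 0.19 |
| vs change, k = 1 | 0.65 | 0.75 | 0.85 | 0.90 | 0.95 |
| vs change, k = 1.25 | 0.78 | 0.89 | 0.98 | 1.00 | 0.95 |
| vs change, k = 0.8 | 0.50 | 0.57 | 0.63 | 0.64 | 0.61 |

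At ρ = 0.8 and equal SDs, 72 adjusted patients carry the information of 72/0.36 = 200 on post scores or 72/0.90 = 80 on change scores, ignoring the cost of the covariate.

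**Power for one pair.** Noncentral t with noncentrality 0.5/√(2V/24), where V is the variance above. Degrees of freedom are 46 for post and change. For the adjusted comparison V is multiplied by 1 + 1/44 and df is 45.

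Worked at ρ = 0.8, k = 1:
- Post: 0.5/√(2/24) = 1.73, power 0.396.
- Change: 0.5/√(0.8/24) = 2.74, power 0.765.
- Adjusted: V = 0.36 × 45/44 = 0.368; 0.5/√(0.736/24) = 2.85, power 0.798.

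| ρ | 0.3 | 0.5 | 0.7 | 0.8 | 0.9 |
|---|---|---|---|---|---|
| Post | 0.396 | 0.396 | 0.396 | 0.396 | 0.396 |
| Adjusted | 0.420 | 0.490 | 0.651 | 0.798 | 0.970 |
| Change, k = 1 | 0.300 | 0.396 | 0.591 | 0.765 | 0.966 |
| Change, k = 1.25 | 0.350 | 0.456 | 0.652 | 0.807 | 0.966 |
| Change, k = 0.8 | 0.243 | 0.316 | 0.469 | 0.618 | 0.858 |

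The gain of adjustment over change scores is 12, 9, 6, 3 and 0 points at k = 1; 7, 3, 0, −1 and 0 at k = 1.25; and 18, 17, 18, 18 and 11 at k = 0.8.

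**With the post-hoc step kept.** Tukey over three pairs in the three-arm model, k = 1, df 69 (adjusted: variance × (1 + 1/67), df 68):

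| ρ | 0.3 | 0.5 | 0.7 | 0.8 | 0.9 |
|---|---|---|---|---|---|
| Post | 0.261 | 0.261 | 0.261 | 0.261 | 0.261 |
| Change | 0.183 | 0.261 | 0.441 | 0.635 | 0.927 |
| Adjusted | 0.283 | 0.347 | 0.508 | 0.680 | 0.936 |

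**Validity.** In simulations of three arms of 24 with no true difference (k = 1, 100,000 trials per ρ), the overall F test and the any-pair Tukey error lay between 0.049 and 0.052 for all three methods. What differs is precision, not error control.

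**The case against.** - **This is a synopsis, and covariates are usual SAP content.** True of a protocol that is silent. This one names one-way ANOVA, which has no covariate by definition, so an SAP that adjusted for baseline would depart from it.
- **If change scores are meant, baseline is already used and the gain may be nil.** This stands as a limit on size. The large gains need the post-score reading. Against change scores the benefit runs from 18 points to a 1-point loss across the cases shown. It does not rescue the plan, which does not say which form is meant.
- **Random allocation is not documented.** This also stands. Study Design says only that patients are divided into three groups. If allocation is not random, the unadjusted comparison risks bias, the power figures do not address that, and analysis of covariance is no guaranteed cure. The case for using baseline would be stronger, not weaker.
- **24 evaluable patients per arm is optimistic.** The 72 are for the whole trial, which has two experiments, and the evaluability criteria remove patients with gaps. Fewer patients would lower the powers under all three methods. The variance ratios do not depend on sample size, apart from the small cost of the covariate.

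**Conclusion.** The point holds as a matter of efficiency. The protocol commits to unadjusted between-group tests while requiring the assessment that would supply the covariate. Under random allocation those tests are valid, and no stated figure is wrong.

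Over post scores the gain for a single pair is 2 points of power at ρ = 0.3, 9 at 0.5, 25 at 0.7, 40 at 0.8 and 57 at 0.9. Over change scores it is modest at equal SDs, substantial when follow-up SD is the smaller, and can vanish when follow-up SD is the larger. In no case examined is adjustment materially worse, and that is the reason to fix it in advance when ρ and the SDs are unknown. All sizes rest on the assumptions listed in the working, and on the inference that the pre-treatment assessment includes the FMA. The change should be made, but the trial's validity does not depend on it if allocation is random.

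**What to change.** For the FMA, replace the between-group t test and one-way ANOVA with:

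> FMA at one post-treatment visit named in advance is compared among the three groups by analysis of covariance, with group as a three-level factor and baseline FMA as covariate. The overall test of group is followed by pairwise differences in adjusted means with Tukey-adjusted p values and simultaneous 95% confidence intervals.

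Holm-adjusted p values are an acceptable alternative. The sponsor has to name the visit; the other post-treatment visits use the same form.

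Consequential points:
- Judge normality on the model residuals, and keep baseline in any non-parametric fallback, for example a rank-based analysis of covariance.
- Use the same form for ARAT with its own baseline.
- Do not extend linear analysis of covariance to MAS, MMT or Brunnstrom stage, taken here to be ordinal grades. No change is proposed for IADLs, whose scoring the protocol does not give.
- State in Criteria for Evaluation that the pre-treatment assessment includes the FMA, if it does.

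The core change is two sentences, with a line or two for the consequential points. It needs no new data and costs one degree of freedom.
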